Terminology Criteria for Adverse Events (CTCAE version 5.0). **Statistical Methods:** Sample size: Sample size was calculated to compare the proportion of participants who become positive to SARS-CoV-2 RT-PCR within 1 month after randomisation between the two groups: Placebo group and experimental group receiving ivermectin up to D28. Based on a study assessing the transmission of SARS-CoV-2 infections in households carried out in the US between April and September 2020, the proportion of randomised participants becoming infected in the placebo group is estimated to be 54% (Grijalva et al, 2020).. A difference of 20% is expected between the two groups (OR=2.28). With a power of 90% (1- β) and a significance level of 5% (α), according to the Casagrande & Pike formula the required sample size to detect such difference with a test of comparison of two proportions is equal to 138 participants per arm (Casagrande et al, 1978). A total of 396 participants (198 per arm), rounded up to 400 participants (200 per arm) is required to account for the primary analysis. This sample size also accounts for an estimated dropout rate of 30%. Primary endpoint analysis: The comparison of proportion of participants who were tested positive for SARS-CoV-2 up to D28: placebo group versus ivermectin group, will be performed using the Cochran-Mantel Haenszel (CMH) chi-squared test at the two-sided 0.05 level. Twosided 95% confidence intervals (95% CI) for the proportion differences between groups will be provided. Odds-ratio and corresponding 95% CI will also be reported. The primary endpoint will also be analysed using a logistic regression with treatment group and country as a covariate. Moreover, the analysis of the primary endpoint will be performed for the PP population.

Clinical Protocol

Safety analysis:

Safety will be pooled analyses for the Safety set from all centres and countries. Placebo and ivermectin groups will be compared.

All adverse events (AEs) will be coded according to coding dictionaries (MedDRA, applicable version) and summarised at System Organ Class (SOC) and Preferred Term (PT) levels. AEs will be classified according to period of occurrence: pre-treatment AEs, treatment-emergent AEs (TEAEs) and post-treatment AEs (PTAEs). AE reporting will focus on TEAEs and PTAEs. Incidence of TEAEs and PTEAEs will be summarised and detailed by seriousness, intensity, action taken with the study medication, other action taken and relationship to study treatment.

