1.3 Study design

This is a randomised, double blind, parallel-group, placebo-controlled, multicentric Phase II clinical trial evaluating the efficacy and safety of ivermectin tablets in the prevention of COVID-19 infection.

If all eligibility criteria are met, the participant will be randomised, and a loading treatment dose will be administered.

Participants will be assigned in a 1:1 ratio to receive oral daily treatment with either ivermectin or placebo. Randomisation will be performed stratified by country.

The study requires two visits to the study center, on Day 1 and Day 28, the first and last days of treatment. In addition, there will be 3 remote visits (day 4, day 7 and day 10) that can be conducted by telephone.

The treatment period lasts for 28 days in total, followed by a 28-day follow-up period, and there is a 2-day window period for visits. Therefore, total study duration for each participant is up to 58 days.

Ivermectin will be supplied as 3 mg tablets and will be administered orally, under fasting conditions, as follows: 200 ug/kg as the loading dose on Day 1 and then 100 ug/kg/day for

Statistical Analysis Plan	Version 1.0		Page 7 of 25
Sponsor	MedinCell	Protocol No	mdc-TTG-CT-002

27 days. Control participants will receive placebo tablets, the number of tablets to be taken will match the number of IVM tablets taken by the active participants in the same body weight range.

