4.1.2 Missing data

In general, an observed cases approach will be applied in case of missing data, i.e., only the observed subject data at a given timepoint will be used.

There will be one notable exception to this rule for the primary efficacy endpoint: if a subject discontinued the study without a confirmed negative test result on D28 (and on any day in between), then the missing data will be imputed using a multiple imputation (MI) method, under the assumption that the results are missing at random (MAR). Details on the MI method can be found in section 4.6.1. The MI method will only be used for the primary efficacy endpoint.

Missing/incomplete information related to AEs and concomitant medications will be handled as listed below, when applicable. Following these steps using temporary programming will ensure that missing date imputation uses the most conservative approach.

In case of a (partially) missing onset date, and the end date is determined to be after the first date of study drug administration, the onset date will be imputed as follows:

• Partially missing onset date:

Statistical Analysis Plan	Version 1.0		Page 11 of 25
Sponsor	MedinCell	Protocol No	mdc-TTG-CT-002

- If the day part is missing and month is equal to month of first study drug administration, then day will be set to day part of first study drug administration date.
- o If the day part is missing and month is not equal to month of first study drug administration, then day will be set to the first day of that month.
- o If both day and month part are missing, and year is not the same as the year of the first study drug administration, then day and month will be set to 1 January.
- o If both day and month part are missing, and year is the same as the year of the first study drug administration, then day and month part will be set to day and month of first study drug administration.
- Complete missing onset date:
 - o If the end date is on or after date of first study drug administration, then the onset date will be set to the date of first study drug administration.
 - o If the end date is prior to the date of first study drug administration, then the onset date does not need an imputation, and the event or medication is considered a pre-treatment AE or prior medication.

In case of a (partially) missing end date, the end date will be imputed as follows:

- In case end date is partially missing:

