4.6 Efficacy

4.6.1 Primary endpoint

The primary endpoint is the proportion of laboratory-confirmed COVID-19 infections between baseline and Day 28. Frequency tables will be provided, and individual results will be listed.

For missing results of the primary endpoint, the multiple imputation (MI) method will be used. MI is performed using 3 general steps: imputation, analysis, and pooling. A total of 10 multiple imputations will be generated using a fully conditional specification (FCS) regression. This method conditions on observed values of the primary outcome measured at other time points (including baseline measurements) and possible other covariates that are related to the missing data pattern and/or primary endpoint. Furthermore, imputations will be performed in each treatment group separately and, if applicable, by stratification factor. The statistical model will be applied to each imputed dataset separately. The estimated parameters from the models will then be pooled using Rubin's combining rules. It should be noted that these combination rules rely on the assumption that the estimated

Statistical Analysis Plan	Version 1.0		Page 14 of 25
Sponsor	MedinCell	Protocol No	mdc-TTG-CT-002

statistics are approximately normally distributed, which may not be the case for the underlying data. Normalizing transformations will then be used on the estimated statistics prior to applying Rubin's rules.

The comparison between the two treatment groups of the proportion of participants will be performed using the Cochran Mantel Haenszel (CMH) chi-squared test. Odds-ratio, relative risk and risk differences and corresponding 95% CI will be reported. Country will be used as a stratification factor. In case the study was only performed in one country, the Chi-squared/Fisher's exact test will be used.

This analysis will be performed based on the mFAS and PP population using the planned treatment

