4.6.3 Further Exploratory endpoints

Factors that may affect the SARS-CoV-2 infection or COVID-19 disease such as sex, age, BMI, and SARS-CoV-2 variant type will be assessed with a logistic regression model with proportion of COVID-19 infections as dependent variable and treatment as independent variable and the factors as covariates. Odds-ratios, 95% CI and P-values will be presented.

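### The SAP does not carry over the protocol's supportive logistic regression on treatment and country, and its exploratory logistic model does not name country (minor)

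*SAP*

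**What the plan says.** **Protocol, synopsis, Statistical Methods.** After the CMH test, the protocol adds a second analysis: "The primary endpoint will also be analysed using a logistic regression with treatment group and country as a covariate".

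**SAP 1.3.** "Randomisation will be performed stratified by country", with 1:1 allocation.

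**SAP 4.6.1.** The comparison of proportions "will be performed using the Cochran Mantel Haenszel (CMH) chi-squared test". "Odds-ratio, relative risk and risk differences and corresponding 95% CI will be reported", and "Country will be used as a stratification factor". There is a fallback: "In case the study was only performed in one country, the Chi-squared/Fisher's exact test will be used". The available text of this section mentions no logistic regression.

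**SAP 4.6.3.** Factors that may affect infection are to be examined in a "logistic regression model with proportion of COVID-19 infections as dependent variable and treatment as independent variable and the factors as covariates". Sex, age, BMI and variant type are given as examples. Country is not named. Odds ratios, confidence intervals and P-values are to be reported.

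**SAP 4.1.2.** Observed cases are the general rule for missing data. Multiple imputation (MI) is the exception: "The MI method will only be used for the primary efficacy endpoint".

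**The concern.** There are three linked gaps.

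1. A supporting analysis of the primary endpoint that the protocol prespecifies is absent from the SAP text, with no reason given. SAP section 5 nevertheless states that the methods were checked for consistency with the protocol.
2. The one logistic model left does not name country, although country stratifies both the randomisation and every CMH comparison. Sex, age and BMI are not randomised. If they differ between countries together with infection risk, a country difference can appear as an age, sex or BMI effect with a P-value attached.
3. The SAP does not say whether 4.6.3 uses the imputed datasets or observed cases. On an observed-case reading, a participant who tests positive and then leaves keeps a known outcome, while one who leaves uninfected has none and is lost.

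At stake are the completeness of the primary-endpoint reporting and the credibility of the exploratory factor odds ratios, not the primary test.

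**Working it through.** **1. The plan's own figures.** With placebo 54% and ivermectin 34%, OR = (0.54/0.46)/(0.34/0.66) = 2.28, as stated. The two-sided Casagrande–Pike formula at 5% and 90% power gives 137.2, so 138 per arm. Then 138/0.70 = 197.1, so 198 per arm. All reproduce, and the point does not affect them. The simulations below use n = 400 × 0.70 = 280 evaluable participants.

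The documents give no infection risks or covariate distributions by country. Every country figure below is therefore an assumption, shown as a range.

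**2. Treatment odds ratio when country is left out.** Assume two equal countries and a within-country OR of 2.28. For each country, ivermectin odds = placebo odds / 2.28. Convert to risks, average over countries, and form the OR of the averages.

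Example, placebo risks 44%/64%:
- placebo odds 0.786 and 1.778; ivermectin odds 0.345 and 0.780; ivermectin risks 25.6% and 43.8%, mean 34.7%
- OR = (0.54/0.46)/(0.347/0.653) = 2.21

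| Placebo risks | OR without country | Shift |
|---|---|---|
| equal, or one country | 2.28 | none |
| 49%/59% | 2.26 | 0.8% |
| 44%/64% | 2.21 | 3.2% |
| 34%/74% | 2.00 | 12% |

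Treatment is balanced within country by design, so this is non-collapsibility of the odds ratio, not confounding.

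**3. Odds ratio of a factor with no true effect.** Assume two equal countries with overall infection risks of 34% and 54%. Let the prevalence of a binary factor be 40% and 60%.
- Risk with the factor: 0.34 × 0.4 + 0.54 × 0.6 = 0.46
- Risk without it: 0.34 × 0.6 + 0.54 × 0.4 = 0.42
- Crude OR = (0.46/0.54)/(0.42/0.58) = 1.18

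At prevalences of 30%/70% the crude OR is 1.39. At equal prevalence it is 1.00. Both the risk and the factor must differ by country.

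**4. False positives for BMI.** Simulation of 1,000 trials per row, n = 280, two equal countries, no true BMI effect, treatment OR 1/2.28 = 0.44, logistic fit on treatment and BMI with and without country:

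| Placebo risks | BMI gap | BMI SD | BMI significant, no country | Treatment OR without / with country |
|---|---|---|---|---|
| 49%/59% | 1 | 4 | 5% | 0.438 / 0.433 |
| 49%/59% | 3 | 4 | 9% | 0.437 / 0.432 |
| 44%/64% | 1 | 4 | 7% | 0.448 / 0.432 |
| 44%/64% | 3 | 4 | 21% | 0.446 / 0.432 |
| 35%/73% | 3 | 4 | 60% | 0.48 / 0.43 |

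With a BMI SD of 4.5 and a gap of 3, the three risk settings give 8%, 18% and 51%. In the extreme setting, adding country brings the false-positive rate to 5% and the BMI odds ratio to 1.00. Variant type is not in these models.

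**5. Observed cases in 4.6.3.** Let p be the infection risk, d the dropout, and f the share of infections that fall after dropout. The observed odds are p(1 − d·f) / ((1 − p)(1 − d)). With no true effect, p = 0.44 in both arms, and assumed dropout of 15% versus 30%:
- f = 0.3: odds 0.883 and 1.021, OR 1.16
- f = 0.5: odds 0.855 and 0.954, OR 1.12

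The arm with more dropout looks worse. With equal dropout the OR is 1.00.

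**The case against.** **Country adjustment of the primary endpoint is already planned.** This stands. A reader might infer that the SAP leaves the treatment effect without any country adjustment. It does not: 4.6.1 stratifies the CMH test by country and reports an odds ratio with its interval. The missing model is supportive and would estimate nearly the same quantity.

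**The model may be recorded elsewhere.** This stands as a caution. Sections 2.2 and 6 of the SAP are not in the text I had, and the last sentence of 4.6.1 has no end there. The full SAP should be checked first.

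**Confounding and attenuation are conditional.** This stands. A reader might infer that the 4.6.3 odds ratios are biased as they are. The documents show neither different risks nor different covariates by country, and they allow for a one-country trial. A false-positive rate above 50% needs the extreme setting.

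**Two treatment odds ratios would not be in conflict.** This stands. They condition on different covariates, and they would still differ with country in 4.6.3.

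**MI may already cover 4.6.3.** This stands in part. SAP 4.1.2 limits MI by endpoint, and the outcome of 4.6.3 is arguably the primary endpoint. That makes the SAP ambiguous rather than wrong, and one sentence would settle it.

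**The stakes are low.** This stands: 4.6.3 is exploratory and its factor list is open, so country is unspecified rather than excluded. An open list does, however, leave the model to be chosen after the data are seen.

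Variant type raises a separate question. If it means the participant's own virus, it has no value for the uninfected, and the changes proposed here do not address that.

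**Conclusion.** The point holds as a minor inconsistency between protocol and SAP. A prespecified supporting analysis is missing from the available SAP text, and the randomisation stratum is not named in the one logistic model that remains. The primary conclusion does not depend on either.

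The numerical effect needs at least two countries with different infection risks and, for the factor odds ratios, different age, sex or BMI distributions as well. For risk gaps of 10–20 points and a BMI gap of 1–3 units, false positives for a null BMI effect run from about 5% to 21% against a nominal 5%. The treatment odds ratio moves toward 1 by about 1–3%, reaching about 12% only for a 40-point risk gap. The observed-case bias (null odds ratio 1.12–1.16) arises only if 4.6.3 is read as observed-case and dropout differs between arms as assumed.

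**What to change.** 1. In SAP 4.6.1, restore the protocol's logistic regression on treatment and country as a supporting analysis, fitted to the same imputed datasets and pooled by Rubin's rules.
2. In SAP 4.6.3, add country as a covariate, omitted if only one country enrols.
3. In SAP 4.6.3, state that the model is run on the imputed datasets of 4.6.1, and adjust the sentence in 4.1.2 to match. The imputation model should then include sex, age and BMI, which the provision for further covariates in 4.6.1 already permits.

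The cost is a few SAP sentences and one model term. No new data are needed. SAP 2.1 already allows an amendment before database lock and unblinding.

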4.7 Safety

All safety analyses will be based on the SS population according to the actual treatment the participant received.

4.7.1 Adverse events

Adverse events will be presented by MedDRA System Organ Class (SOC) and Preferred Term (PT). Coding of verbatim terms has been performed either by Ergomed or the Sponsor and that all relevant codes are stored in the database.

Adverse events will be classified according to period of occurrence: pre-treatment AEs, treatment-emergent AEs (TEAEs) and post-treatment AEs (PTAEs).

- Pre-treatment AEs are defined as adverse events starting before the first study drug intake.
- TEAEs (i.e. during the treatment period) are defined as AEs starting from the first study drug intake until three days after the last study drug intake.
- Post-treatment AEs are defined as AEs starting four days after the treatment period (last study drug intake).

AE reporting will focus on TEAEs and PTAEs. Pre-treatment AEs will only be listed.

Frequency tables of participants experiencing at least one occasion of the event while at risk (along with the number of different occurrences of the TEAE), will be presented for the following types of adverse events:

- All TEAEs and PTAEs irrespective of the causality assessment
- TEAEs and PTAEs by CTCAE grade
- TEAEs and PTAEs by action taken with the study medication
- Related TEAEs and PTAEs
- Serious TEAEs and PTAEs (SAEs)
- Related serious TEAEs and PTAEs
- Fatal TEAEs or PTAEs

[figure not shown]
Statistical Analysis Plan	Version 1.0		Page 17 of 25
Sponsor	MedinCell	Protocol No	mdc-TTG-CT-002

Participants will only be counted once within a PT or SOC.

SOC terms will be presented according to the Internationally Agreed Sorting Order (MedDRA).

Comparison between the treatment groups on the number of participants with TEAEs/PTAEs will be performed by means of a Fisher's exact test.

Detailed listings of all fatal and other serious events will be provided (for section 14.3.2). Narratives will not be included in section 14.3.3 but will be provided by medical writing in section 12.3.2 of the CSR. All adverse events (i.e. TEAEs as well as non-treatment emergent events) will be listed in section 16.2 of the CSR. However, only TEAEs and PTAEs will be summarized in the tables.

Statistical Analysis Plan	Version 1.0		Page 18 of 25
Sponsor	MedinCell	Protocol No	mdc-TTG-CT-002

Statistical Analysis Plan	Version 1.0		Page 19 of 25
Sponsor	MedinCell	Protocol No	mdc-TTG-CT-002

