RT-PCR tests on D4, D7, D10, and D28, and at any unscheduled visits. Secondary endpoints analyses: RT-PCR tests on D4, D7, D10, and D28, and at any unscheduled visits. WHO COVID-19 and News 2 scales scoring on D1, D10, and D28, and at any unscheduled visits. COVID-19 related AE notification by participants and/or investigators throughout the study. COVID-19 related hospitalisations notified by the investigators. Duration of hospitalisation as calculated from the associated SAE notification form (date of hospital admission through to date of hospital release). COVID-19 related deaths notified by the investigators. AE notification by participants or detection by investigators. **Concomitant Medication:** Prohibited medications: The following medications are prohibited: Inhibitors of p-glycoprotien, e.g. amiodarone, azithromycin, ketoconazole, cyclosporine up to 28 days prior to randomization and throughout the study. Current pain medications such as acetylsalicylic acid or metamizol. Precautions: Some medications may have moderate or minor interactions with ivermectin. **Endpoints:** Primary endpoint: Proportion of laboratory-confirmed COVID-19 infections between baseline and Day 28. Secondary endpoints: Time to change from baseline in negative RT-PCR to positive RT-PCR. Change from baseline in the WHO-COVID 19 and NEWS-2 scores. Time to change from baseline to first COVID-19 related clinical events. Proportion of COVID-19 related hospitalisations. Proportion of COVID-19 related mortality. Safety and Tolerability of ivermectin based on treatment emergent adverse events (TEAE) and serious adverse events (SAE) according to Common

Clinical Protocol

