The number/frequency of participants with TEAEs, related TEAEs, PTAE, the number/frequency of participants with related PTAEs, SAEs and CTCAE grade 3 or more will be displayed by system organ class and preferred term according to MedDRA classification. The frequency of participants with at least one TEAE, PTAE, related PTAE, SAE and/or AE of CTAE grade 3 or more will be compared between treatment groups using a chi-squared test or a Fisher exact test.

Table 1: Schedule of Assessments

	Pre Screening D-1 or D1*	Screening & Randomisation	On-treatment period (i)				EOS (J)
		D1	D4 (±1 day)	D7 (±1 day)	D10 (±1 day)	EOT-D28** (+2 days)	D56 (±2 days)
	Remote	On-site Visit***	Remote	Remote	Remote	On-site Visit***	Remote
Study participation suitability questionnaire (a)	X						
ICF signature (b)		X					
Demographics		X					
Medical history		X					
I/C criteria		X					
Treatment dispensation		X					
Treatment administration (c)						-	
RT-PCR test (d)		X	X	X	X	X	
Antigen test (e)		X					
Serology (f)		X				X	X
NEWS-2 scale		X			X	X	
COVID-19 WHO scale		X			X	X	
Laboratory tests (g)		X				X	X
Urine pregnancy test (g)		X				X	X
Randomisation		X					
Participant diary (i)						•	
ECG		X				X	
Vital signs		X			X	X	
Adverse Events			· -				
Concomitant medication							

Clinical Protocol

- * Pre-Screening corresponds to the time frame when the first positive case is detected in the cluster within 5 days prior to screening. The study is immediately proposed to the exposed cluster members who might potentially meet the eligibility criteria (Note: only one member in the same household will be enrolled).
- ** Preferred on-site visit but can be performed remotely according to the investigator's opinion.
- *** In case of on-site visit, participants should only use private transport. Moreover, a specific room for participants has to be available and restricted to participants in order to limit their contact with patients.
- a) Participants will be questioned about their close contact to the COVID-19 index case, their interest in participating in the study, and will be given information about the study (note that full eligibility inclusion/exclusion criteria will be confirmed once the participant has signed an ICF).
- (b) ICF signature for the participant and the index case to collect information regarding his/her SARS-CoV-2 RT-PCR test results,

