1.4 Planned sample size

The sample size was calculated to compare the proportion of participants who become positive to SARS-CoV-2 RT-PCR within 1 month after randomisation between the two groups: Placebo group and ivermectin group. The assumptions are based on results of a study assessing the transmission of SARS-CoV-2 infections in households carried out in the US between April and September 2020. Thus it is expected that the proportion of participants becoming infected in the placebo group is 54% or higher (Grijalva et al, 2020). Furthermore, a reduction by 20% is expected in the ivermectin group (OR=2.28).

When requiring a power of 90% (1- β) and a significance level of 5% (α), then according to the Casagrande & Pike formula the required sample size to detect such difference with a test of comparison of two proportions is equal to 138 participants per treatment arm (Casagrande et al, 1978).

A total of 396 participants (198 per arm), rounded up to 400 participants (200 per arm) is required to account for an estimated rate of randomised participants who won't be valued for the primary analysis of 30%.

[figure not shown]

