4 STATISTICAL ANALYSES

All statistical analyses will be performed using the SAS® software (Version 9.4 or later, SAS institute, North Carolina, USA).

All descriptive statistics will be given by treatment group. For baseline and basic variables, they will also be given for the entire analysis set. Screening failure data will not be analysed.

If not stated otherwise the following standard types of descriptive analyses will be presented:

- Descriptive statistics for continuous data

Statistical Analysis Plan	Version 1.0		Page 10 of 25
Sponsor	MedinCell	Protocol No	mdc-TTG-CT-002

N, mean, SD, min, lower quartile, median, upper quartile, and max will be presented. These descriptive statistics will be determined for measured values and optionally for differences to baseline.

Descriptive statistics for categorical data

Absolute frequencies and percentages will be presented. Percentage bases (denominators) will be identified in the table title or footnote (i.e. all subjects at risk, all cases). For changes from baseline, shift tables may be generated.

Inferential statistics

Unless otherwise stated, all statistical tests will be performed two-sided and at a type I error probability of α =0.05.

Unless otherwise stated, all confidence intervals (CIs) will be derived two-sided and at a confidence probability of $1-\alpha=0.95$.

Listings

All recorded data will be listed by subject sorted by treatment group. Identification variables are centre number, participant number and treatment.

Derived data will be stored in special analysis data sets and will be calculated as outlined in section 6.1.

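### The adverse-event comparison in SAP 4.7.1 counts COVID-19 illness, so a fall in infections could attenuate, hide or reverse a drug-caused excess of adverse events

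*SAP*

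**What the plan says.** SAP 4.7.1 classifies adverse events by period. A TEAE is any AE that starts between the first intake and three days after the last; later ones are PTAEs. No exception is made for COVID-19. The section lists frequency tables (all events, by CTCAE grade, by action taken, related, serious, related serious, fatal) and then gives one sentence on testing: "Comparison between the treatment groups on the number of participants with TEAEs/PTAEs will be performed by means of a" Fisher's exact test. It does not say whether this is one test of any event or a test for each table.

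The protocol synopsis, under the evaluation criteria, collects "COVID-19 related AE notification by participants and/or investigators throughout the study". Its safety analysis names more comparisons than the SAP sentence does. Besides TEAEs and PTAEs it says that "related PTAE, SAE and/or AE of CTAE grade 3 or more will be compared between treatment groups", by chi-squared or Fisher test.

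The safety set (SAP 3.2) is everyone who took at least one tablet. Neither document, in the text reviewed, describes an AE summary or test with COVID-19 events set apart.

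**The concern.** In a prevention trial the disease to be prevented also produces adverse events. If the drug works, the placebo arm collects more of them, and a count of participants with any event mixes two opposite effects: fewer infections and whatever the drug itself causes. A null or favourable result could then be read as evidence that 28 days of dosing is well tolerated when it partly reflects efficacy. Safety and tolerability is a stated objective, and the participants are healthy volunteers.

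Tables by preferred term help only in part. The protocol's list of typical COVID-19 symptoms (exclusion criterion 4) includes headache, myalgia and cough, which are non-specific and could also be reported as drug effects.

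**Working it through.** **The plan's own figure first.** SAP 1.4 expects that "the proportion of participants becoming infected in the placebo group is 54% or higher". The protocol adds: "A difference of 20% is expected between the two groups (OR=2.28"). The odds ratio fixes the reading as absolute: (0.54/0.46)/(0.34/0.66) = 2.279, so the design is 54% vs 34%. With two-sided 5%, 90% power and 1:1 allocation:

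- Uncorrected n = [1.96·√(2·0.44·0.56) + 1.2816·√(0.54·0.46 + 0.34·0.66)]² / 0.20² = 127.4, that is 128.
- With the Casagrande & Pike correction: (127.4/4)·[1 + √(1 + 4/(127.4·0.20))]² = 137.2, that is 138.
- 138/0.70 = 197.1, that is 198 per arm, rounded in the plan to 200.

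The stated sample size reproduces, so 54% and 34% are used below. The safety set needs only one tablet, so 200 per arm is taken as its size.

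**Assumptions, none given in the documents.** b is the risk of a non-COVID TEAE on placebo, e is the drug-caused excess in percentage points, and s is the share of infections recorded as a TEAE. Non-COVID events and infection are taken as independent.

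**Formulae.**

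- Placebo: P(any TEAE) = 1 − (1 − b)(1 − 0.54s)
- Ivermectin: P(any TEAE) = 1 − (1 − b − e)(1 − 0.34s)

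For example, with b = 20%, e = 10 points and s = 50%, placebo is 1 − 0.80 × 0.73 = 41.6% and ivermectin is 1 − 0.70 × 0.83 = 41.9%.

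Power is for the two-sided Fisher exact test at 5%, by full enumeration at 200 per arm, counting only significant results with more events on ivermectin.

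| Events counted (b = 20%, e = 10 points) | Placebo | Ivermectin | Power to show the excess |
|---|---|---|---|
| Non-COVID only | 20.0% | 30.0% | 60% |
| All, s = 25% | 30.8% | 36.0% | 17% |
| All, s = 50% | 41.6% | 41.9% | 2% |
| All, s = 70% | 50.2% | 46.7% | 0.3% |
| All, s = 100% | 63.2% | 53.8% | under 0.1% |

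In the last row there is a 43% chance of a significant result in favour of ivermectin.

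**Break-even excess.** The two all-TEAE rates are equal when e = (1 − b)[1 − (1 − 0.54s)/(1 − 0.34s)]. A smaller excess changes sign; a larger one is attenuated.

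| s | b = 20% | Range over b = 40% to 10% |
|---|---|---|
| 25% | 4.4 points | 3.3 to 4.9 |
| 50% | 9.6 | 7.2 to 10.8 |
| 75% | 16.1 | 12.1 to 18.1 |
| 100% | 24.2 | 18.2 to 27.3 |

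**Where the effect is weaker (b = 20%).**

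- An excess of 15 points: power is 91% on non-COVID events and 49%, 12% and 1% on all events at s = 25%, 50% and 75%.
- An excess of 20 points with s = 25%: 99% on non-COVID events and still 81.5% on all events.
- Placebo infection of 10% at the same odds ratio (10% vs 4.6%): the break-even excess is only 1.1 to 4.5 points for s = 25% to 100%.
- No effect on infection (54% in both arms): the difference is e(1 − 0.54s). A 10-point excess becomes 7.3 points at s = 50%. It shrinks but cannot change sign.

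**The case against.** The strongest reply has four parts.

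*The size is conditional.* Masking needs the drug to work and needs infections to become AEs. Infection is sought by scheduled RT-PCR on D4, D7, D10 and D28, which can find symptomless cases, so s may be low. This stands. A reader might infer that the planned test will necessarily hide or reverse a drug-caused excess. The documents do not support that, because they give none of b, e and s.

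*The test sentence may cover every table.* It follows a list that includes related, serious and CTCAE-grade events, and the protocol names SAEs and grade 3 or more for comparison. A reader might infer that the SAP has only one all-cause test and has dropped the others. That is one reading; what can be shown is that the scope is not stated. On either reading, no listed table separates COVID-19 events, and the SAE and grade 3 counts contain them too.

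*Other outputs would show drug effects.* The related-event and SOC/PT tables do give information, and COVID-19 clinical events and hospitalisations are endpoints in their own right. But relatedness is a causality judgement, related TEAEs are not in the protocol's list of comparisons, and non-specific symptom terms remain mixed.

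*The all-TEAE test is valid and the alternative has its own bias.* This stands. Comparing all events estimates the net effect, so saying that TEAEs are no more common in a 41.6% vs 41.9% result would be true as stated. Removing COVID-19 events can also mislead. Suppose there is no drug effect on other events, a 20% background, and half of infected participants' other AEs wrongly flagged. The rates become 20% × (1 − 0.54 × 0.5) = 14.6% vs 20% × (1 − 0.34 × 0.5) = 16.6%, a spurious excess on ivermectin that blinding does not remove. The excluded comparison therefore belongs beside the all-TEAE test, not in its place.

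**Conclusion.** The point holds in conditional form. As written, the AE comparison includes the efficacy outcome, and under the design's own infection rates it leans towards ivermectin. A 10-point excess (20% vs 30%) would be roughly halved if a quarter of infections give an AE, cancelled at about half, and reversed above that. This rests on the assumed b, e and s, on independence, and on the planned effect on infection being real.

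The safety set adds some dilution. Unlike the mFAS (SAP 3.4), it is not restricted to participants with a confirmed negative baseline RT-PCR, so symptoms that start after the first dose in someone already infected also count as TEAEs.

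The conclusion covers the text reviewed: SAP 4.7.1 contains a figure that is not shown, SAP section 6.1 on derived data is cited but was not available, and the protocol was available only as synopsis and schedule. A rule for COVID-19 events could sit in one of these. The change is a worthwhile, inexpensive improvement; the planned test is not invalid.

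**What to change.** In SAP 4.7.1:

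1. Keep the all-TEAE/PTAE comparison. Beside it, add a Fisher comparison of participants with at least one TEAE/PTAE that is not COVID-19 related. Define this by the COVID-19-related flag, or by a list of terms, fixed before unblinding.
2. Report both, with a note that the first estimates the net effect on adverse events and that misflagging in the arm with more infections can bias the second.
3. State which tables the Fisher test covers. Include SAEs and CTCAE grade 3 or more, as the protocol plans, each with and without COVID-19 events.

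The cost is a few extra table rows and reliance on a blinded judgement of COVID-19 relatedness. The trial already has to make that judgement for its endpoint of time to first COVID-19 related clinical event.
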